## 8.4 Analysis Sets

The analysis sets are defined in [Table 10](#). The analysis sets may be defined for Part 1 and Part 2 separately.

**Table 10: Analysis Sets**

Analysis Set	Description
Randomization Set	Part 2: All participants who are randomly assigned, regardless of the participants' treatment status in the study.
Full Analysis Set (FAS)	Part 1: All enrolled participants in Part 1 who receive at least 1 injection of IP. Part 2: All randomly assigned participants who receive at least 1 injection of IP. Part 3: All enrolled participants in Part 3 who receive at least 1 injection of IP.
Per Protocol (PP) Set	All participants in the FAS who receive planned doses of IP per schedule, comply with the immunogenicity schedule, and have no major protocol deviations that impact key or critical data. Participants who are RT-PCR positive or seropositive at baseline will be excluded from the PP Set. The PP Set in Part 1 will be used for all analyses of immunogenicity in Part 1 unless specified otherwise.
Immunogenicity Subset	A subset of participants in the FAS will be selected for immunogenicity sampling and testing.
Per Protocol Immunogenicity Subset	A subset of participants in the FAS will be selected for immunogenicity testing. The PP Immunogenicity Subset includes participants selected for the Immunogenicity Subset who receive planned doses of IP per schedule, comply with immunogenicity testing schedule, and have no major protocol deviations that impact key or critical data. Participants who are RT-PCR positive or seropositive at baseline will be excluded from the PP Immunogenicity Subset, in addition to participants with HIV who are receiving highly active anti-retroviral therapy (HAART). The PP Immunogenicity Subset will be used for all analyses of immunogenicity unless specified otherwise.
Safety Set	All enrolled participants (in Part 1 and Part 3) and all randomly assigned participants (in Part 2) who receive at least 1 dose of IP. The Safety Set will be used for all analyses of safety except for solicited ARs. Safety Set for the booster/third dose phase will include all participants who receive a booster dose or third dose.
Solicited Safety Set	The Solicited Safety Set consists of participants in the Safety Set who contributed any solicited AR data. The Solicited Safety Set will be used for the analyses of solicited ARs.
Modified Intent-to-Treat (mITT) Set	All participants in the FAS who have no serologic or virologic evidence of prior SARS-CoV-2 infection before the first dose of IP (both negative RT-PCR test for SARS-CoV-2 and negative serology test based on bAb specific to SARS-CoV-2 nucleocapsid) at baseline.

Analysis Set	Description
Modified Intent-to-Treat-1 (mITT1) Set	All participants in the mITT Set excluding those who received the wrong treatment (ie, at least 1 dose received that is not as randomized or planned).
Per Protocol Immunogenicity Subset for booster dose or third dose phase	The PP Immunogenicity Subset for booster dose or third dose phase includes participants who received planned booster dose or third dose per schedule, complied with immunogenicity testing schedule, and have no major protocol deviations that impact key or critical data, with pre-booster or pre-third dose negative or positive SARS-CoV-2. The PP Immunogenicity Subset with pre-booster pre-third dose negative SARS-CoV-2 will be used for the primary immunogenicity analysis.

Abbreviations: AR = adverse reaction; bAb = binding antibody; FAS = full analysis set; HAART = highly active anti-retroviral therapy; HIV = human immunodeficiency virus; IP = investigational product; mITT = modified intent-to-treat; mITT1 = modified intent-to-treat-1; PP = per protocol; RT-PCR = reverse transcriptase polymerase chain reaction; SARS-CoV-2 = severe acute respiratory syndrome coronavirus 2.

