## **5.4 Study Treatment Compliance**

All doses of IP will be administered at the study site under direct observation of medically qualified study staff and appropriately recorded (date and time) in the eCRF. Qualified study site staff will confirm that the participant has received the entire dose of IP. If a participant does not receive IP or does not receive all of the planned doses, the reason for the missed dose will be recorded. Data will be reconciled with study site accountability records to assess compliance.

Participants who miss the second dose due to noncompliance with the visit schedule and not due to a safety pause will still be required to follow the original visit and testing schedule as described in the protocol and their regimen schedule. Unless consent/assent is withdrawn, a participant who withdraws or is withheld from receiving the second dose will remain in the study and complete all safety and immunogenicity assessments required through the participant's last scheduled study visit.

The study site staff are responsible for ensuring that participants comply with the allowed study visit windows. If a participant misses a visit, every effort should be made to contact the participant and complete a visit within the defined visit window. If a participant does not complete a visit within the time window, that visit will be classified as a missed visit and the participant will continue with subsequent scheduled study visits. All safety requirements of the missed visit will be captured and included in the subsequent visit.

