### COVID-19:

To be considered as a case of COVID-19 for the evaluation of the efficacy endpoint, the following case definition must be met:

- The participant must have at least 1 nasal swab (or respiratory sample, if hospitalized) positive for SARS-CoV-2 by RT-PCR AND
- ONE of the following:
  - Fever (temperature  $\geq 38^{\circ}\text{C}/\geq 100.4^{\circ}\text{F}$ ) or chills (of any duration, including  $\leq 4$  hours)
  - Shortness of breath or difficulty breathing (of any duration, including  $\leq 48$  hours)
  - Cough (of any duration, including  $\leq 48$  hours)
  - Fatigue
  - Muscle or body aches
  - Headache
  - New loss of taste or smell
  - Sore throat
  - Congestion or runny nose
  - Abdominal pain
  - Nausea or vomiting
  - Diarrhea

- Poor appetite/poor feeding

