#### SARS-CoV-2 Infection:

- SARS-CoV-2 infection is defined in participants with SARS-CoV-2 negative at Baseline:
  - bAb level against SARS-CoV-2 nucleocapsid protein negative at Day 1 that becomes positive (as measured by Roche Elecsys) post Baseline, OR
  - Positive RT-PCR post Baseline

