#### **8.5.4 Efficacy Analysis**

To evaluate the incidence of COVID-19 after vaccination with mRNA-1273 or placebo, the incidence rate will be provided by vaccination group, dose level, and age group, calculated as the number of cases divided by the total person-time. Participants in Part 1 and Part 2 of the study and in different age groups who receive the same mRNA-1273 dose level (if applicable) may be combined in the analysis.

For serologically confirmed SARS-CoV-2 infection or COVID-19, regardless of symptomatology or severity, infection rate will be provided by vaccination group, dose level, and age group. The same analysis will be conducted for asymptomatic SARS-CoV-2 infection.

The secondary efficacy analyses will be performed on the PP Set, with sensitivity analyses in FAS, modified Intent-to-Treat (mITT) Set, and modified Intent-to-Treat-1 (mITT1) Set. Analyses of the efficacy endpoints in Part 2 will be performed for the randomized blinded phase. Additional exploratory analyses will be conducted in the blinded and unblinded phases for participants randomized to mRNA-1273 in Part 2, and in the unblinded phase for participants who are originally randomized to the placebo arm and cross-over to mRNA-1273 after use of any COVID-19 vaccine is authorized or licensed for the participant's age group.

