10. On Day 1, sample must be collected prior to randomization and dosing. On Day 29, sample must be collected prior to dosing. In Part 2, participants in each age group will be assigned to 1 of 5 phlebotomy cohorts ([Table 14](#)). Participants in 3 of these 5 cohorts will provide blood specimens for immunogenicity at the following time points: Day 1, Day 57, and one of Day 29, Day 209, or Day 394 (such that each participant provides a total of 3 blood samples only). Participants in the Cohort D (remainder of the age group) will provide a blood sample at Day 1 (prior to randomization and the first dose) and within 4 days of receiving Dose 2 at Day 30 (+3 days) for storage and potential future biomarker testing. A fifth cohort of participants (selected VTEU sites only) will provide blood samples for assessment of exploratory serology and CMI (S protein-specific T-cell responses) on Day 1, Day 43, Day 209, and D394. [Table 14](#) provides the blood sampling schedule in Part 2 of the study. If a Day 1 (baseline) blood sample cannot be obtained in either Part 1 or Part 2, the participant will be considered either a screen failure due to inability to satisfy inclusion criterion 3 or could be rescheduled for rescreening. Participants may be rescreened 1 time, either within the same screening period for Part 1 or Part 2 or in a new screening period of Part 2 if the initial screening was in Part 1. If the participant is rescreened and a blood sample still cannot be obtained, then he/she will be considered a screen failure due to inability to satisfy inclusion criterion 3.
11. Part 2, Cohort D participants only, one ~4 mL blood draw. For participants already enrolled in Cohort D prior to Protocol Amendment 4, this blood draw will be optional and confirmed at time of re-consenting; for all participants newly enrolled into Cohort D under Amendment 4, it is mandatory.
12. The nasal swab sample (collected before dosing on injection day) will be used to ascertain the presence of SARS-CoV-2 via RT-PCR.
13. An unscheduled visit may be prompted by reactogenicity issues or new or ongoing AEs.

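### The main set for the secondary efficacy analyses requires compliance with the immunogenicity schedule, so a valid COVID-19 case can leave the main incidence analysis over a blood draw

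*Protocol*

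**What the plan says.** - **Set definition.** Table 10, and the same table in the synopsis, defines membership of the PP Set as follows: "All participants in the FAS who receive planned doses of IP per schedule, comply with the immunogenicity schedule, and have no major protocol deviations". The deviations meant are those that touch key or critical data. Children who are RT-PCR positive or seropositive at baseline are excluded. The only use that Table 10 names for this set is Part 1 immunogenicity.
- **Use for efficacy.** Section 8.5.4, and the synopsis, state: "The secondary efficacy analyses will be performed on the PP Set, with sensitivity analyses in FAS, modified Intent-to-Treat (mITT) Set". The mITT1 Set is named there as well. No PP Set for efficacy is defined. Section 8.4 allows sets to be defined separately for Part 1 and Part 2, but gives no efficacy version.
- **Incidence measure.** COVID-19 incidence is "calculated as the number of cases divided by the total person-time".
- **COVID-19 case.** Section 7.3.1 requires "The participant must have at least 1 nasal swab (or respiratory sample, if hospitalized) positive for SARS-CoV-2 by RT-PCR", together with one listed symptom.
- **SARS-CoV-2 infection.** Section 7.3.1 accepts either of two routes. The first is serological: "bAb level against SARS-CoV-2 nucleocapsid protein negative at Day 1 that becomes positive (as measured by Roche Elecsys) post Baseline, OR". The second is a positive RT-PCR after baseline.
- **Missed visits.** Section 5.4: "If a participant does not complete a visit within the time window, that visit will be classified as a missed visit". The child then carries on with later visits.
- **Who is bled.** Table 12, footnote 10: "participants in each age group will be assigned to 1 of 5 phlebotomy cohorts". Under Table 14, Cohorts A-C have a Day 57 draw and one of Day 29, 209 or 394. Cohort E (24 children) is drawn on Days 43, 209 and 394. Cohort D, the remainder, has only a stored biomarker sample after baseline.

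**The concern.** The PP Set was written for immunogenicity, where a sample outside its window is a good reason to leave a child out. The same clause then governs the main analysis of an endpoint that does not use blood. For symptomatic RT-PCR-confirmed COVID-19, a late or absent draw says nothing about whether a case would have been found. Such a child can have received both doses, been negative at baseline and stayed under follow-up, and still contribute neither case nor person-time to the main result.

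The condition acts after randomisation, and the documents contain a route by which it could depend on outcome. Section 3.1.1 replaces a site visit with a telemedicine visit when a child cannot attend because of the pandemic, self-quarantine included, and a telemedicine visit cannot collect blood. If infection or exposure makes a missed draw more likely, cases are removed more often than non-cases, and both incidence and the absolute vaccine-placebo difference are too low in the main analysis.

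**Working it through.** **1. The plan's own non-compliance figure.** Section 8.3 assumes that about 25% of the Immunogenicity Subset will not qualify for the PP Immunogenicity Subset, with about 396 vaccinees selected to give about 289.

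- 289 / (1 - 0.25) = 385.3, rounded up to 386, against 396 stated.
- 396 x 0.75 = 297, against 289 stated.

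Both agree within 3%, so 25% is a usable planning rate. It covers all causes, including baseline positives and dosing deviations.

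**2. Reach in Part 2, per age group.** Table 14 gives Cohorts A-C as 3 x 176 = 528 and Cohort E as 24, so 552 in total. Section 5.2 gives up to 4,000 per age group. Section 3.1 also gives about 1,700 for ages 6 to < 12 years, so both sizes are shown.

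| | N = 4,000 | N = 1,700 |
|---|---|---|
| Cohorts A-C and E: 552 / N | 13.8% | 32.5% |
| Cohort D: (N - 552) / N | 86.2% | 67.5% |
| Removed at 25%: 0.25 x 552 = 138, / N | 3.5% | 8.1% |
| Cohorts A-C only: 0.25 x 528 = 132, / N | 3.3% | 7.8% |

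The last two rows are upper bounds if the 25% rate holds, because part of that 25% would be excluded anyway. Applying 25% to Cohort E is an assumption, since that cohort is outside the 528.

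**3. Effect on incidence if missed draws are linked to illness (assumed rates).** The documents give no miss rate by case status. Assume that 5% of non-cases and 20% to 50% of cases in the 552 miss a draw, that cases are rare, and that person-time per child is similar. With f = 552 / N and c = the proportion of cases lost:

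retained incidence / true incidence = [(1 - f) + f(1 - c)] / [(1 - f) + 0.95f]

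- N = 4,000 (f = 0.138): 0.9724 / 0.9931 = 0.979 at c = 0.20; 0.9310 / 0.9931 = 0.937 at c = 0.50. Understatement is about 2% to 6%.
- N = 1,700 (f = 0.325): about 0.950 at c = 0.20 and 0.851 at c = 0.50. Understatement is about 5% to 15%.

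If cases and non-cases miss draws equally, the factor is 1 and only precision is lost.

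**4. Effect on the comparison (assumed attack rates).** Take the worst case above (c = 0.50) within the affected cohorts, equal in both arms, with true risks of 10% on placebo and 3% on vaccine.

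- Placebo: 0.10 x 0.50 / (0.10 x 0.50 + 0.90 x 0.95) = 0.0500 / 0.9050 = 5.52%.
- Vaccine: 0.03 x 0.50 / (0.03 x 0.50 + 0.97 x 0.95) = 0.0150 / 0.9365 = 1.60%.
- Ratio: 0.30 becomes 1.60 / 5.52 = 0.29.
- Difference: 7.0 points becomes 3.9 points, in the affected cohorts only.

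The absolute measures move and the ratio barely does.

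**The case against.** The strongest reply is that the plan already carries the remedy. FAS, mITT and mITT1 have no blood-draw condition and are all named as sensitivity analyses. mITT1 is baseline-negative and excludes wrong treatment, which is close to what an efficacy PP Set would be. This stands as a limit on the harm. A reader might infer that these cases vanish from the efficacy results, but they leave only the main one.

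Second, the draws are not irrelevant to every efficacy endpoint. Infection and asymptomatic infection can be met by nucleocapsid serology, and swabs are taken at the same visits. That stands too, and it confines the full objection to symptomatic COVID-19. It does not justify removing the whole child, because RT-PCR alone can establish infection.

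Third, a reader might infer a bias against the vaccine. The documents do not support that as a general claim. Allocation is 3:1 within each cohort in Table 14, so the condition falls on both arms in proportion, and equal case-dependent loss leaves the ratio nearly intact (step 4).

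Fourth, missed draws are mitigated. Home visits are allowed for all nondosing visits other than Screening, and Table 14 gives the Day 209 and Day 394 draws a further 30 days. Home visits do need IRB permission, consent and Sponsor approval, so the route to a missed draw is narrowed but not closed.

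Fifth, the operational rule for compliance belongs in the SAP. That is fair as to which draws count. It does not cover the protocol's own choice to place efficacy on a set with this condition.

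**Conclusion.** The mismatch is real and modest. The clause has no bearing on ascertaining symptomatic RT-PCR-confirmed COVID-19, yet it decides who enters that endpoint's main analysis. In Part 2 it reaches 13.8% of a 4,000-child age group (32.5% of 1,700) and removes at most about 3.5% (8.1%), assuming that the plan's 25% exclusion rate applies to all 552 children. Any bias in incidence or the absolute difference depends on missed draws being tied to illness, which the documents make possible but do not quantify. The 2% to 6% understatement (5% to 15% at 1,700) rests on assumed miss rates.

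Two stronger readings should be resisted. The 13.8% is the share that carries the condition, not the share lost. A reader might also take compliance to require post-baseline immunogenicity samples, which would remove all of Cohort D (86.2%). Table 10 does not say this, and a child with no such draw scheduled is more naturally read as compliant.

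The endpoints are secondary and carry no hypothesis test. The primary immunogenicity conclusions and the three sensitivity sets are untouched.

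**What to change.** - Add a PP Set for Efficacy to Table 10 and to the synopsis table: negative at baseline, planned doses received, no major deviation affecting the efficacy endpoint, and no immunogenicity-schedule condition.
- Cite that set in Section 8.5.4 and in the synopsis efficacy paragraph in place of the present PP Set.
- For the serology-based infection endpoints, treat a missing draw as missing serology and keep the child in the set, since RT-PCR alone can meet the definition.
- Keep the blood-draw condition for the immunogenicity sets only.

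The cost is one table row and one reference, each mirrored in the synopsis, plus a sentence on missing serology. No new data are needed, and FAS, mITT and mITT1 stay as they are.

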## 8.5 Statistical Methods

### 8.5.1 Baseline Characteristics and Demographics

Demographic variables (eg, age, race, ethnicity) and baseline characteristics (eg, length/height, weight, and BMI) will be summarized by treatment group. Summary statistics (mean, standard deviation for continuous variables, and number and percentage for categorical variables) will be provided.

### 8.5.2 Safety Analyses

All safety analyses will be based on the Safety Set, except summaries of solicited ARs, which will be based on the Solicited Safety Set. All safety analyses will be provided by vaccination group (dose levels of mRNA-1273 and placebo) and by age group. Participants in Part 1 and Part 2 of the study and in different age groups who receive the same mRNA-1273 dose level may be combined for safety analysis.

Safety and reactogenicity will be assessed by clinical review of all relevant parameters including solicited ARs (local and systemic events), unsolicited AEs, SAEs, MAAEs, AESIs, AEs leading to discontinuation, and physical examination findings.

The number and percentage of participants with any solicited local AR, with any solicited systemic AR, and with any solicited AR during the 7-day follow-up period after each injection by toxicity grade will be provided. A 2-sided 95% exact CI using the Clopper-Pearson method will also be provided for the percentage of participants with any solicited AR.

The number and percentage of participants with unsolicited AEs, SAEs, MAAEs, severe AEs, and AEs leading to discontinuation from IP or withdrawal from the study will be summarized. Unsolicited AEs will be presented by MedDRA preferred term and system organ class.

The number of events of solicited ARs, unsolicited AEs/SAEs, and MAAEs will be reported in summary tables accordingly.

Solicited AR events (starting within 7 days after any injection) that are serious or lasting beyond Day 7 after any injection will also be reported as unsolicited AEs.

For all other safety parameters, descriptive summary statistics will be provided, and [Table 11](#) summarizes the analysis strategy for safety parameters. Further details will be described in the SAP.

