## 3 STUDY DESIGN

### 3.1 General Design

This is a Phase 2/3, three-part, open-label, dose-escalation, age de-escalation and randomized, observer-blind, placebo-controlled expansion study intended to infer the effectiveness of mRNA-1273 in children aged 6 months to < 12 years. The study population will be divided into 3 age groups (6 years to < 12 years, 2 years to < 6 years, and 6 months to < 2 years), and up to 3 dose levels (25, 50, and 100 µg) of mRNA-1273 will be evaluated (and a third dose or an optional booster of 10 or 25 µg).

The study will be conducted in 3 parts. Part 1 of the study will be open-label and consist of dose-escalation and age de-escalation in approximately 1,275 participants to select the dose for each age group with the highest number enrolled in the oldest age group ([Table 3](#)). Part 2 of the study will be a placebo-controlled observer-blind evaluation of the selected dose in up to 12,000 participants (up to 4,000 participants each in the 6 years to < 12 years, 2 years to < 6 years, and the 6 months to < 2 years of age groups). Part 3 will be an open-label alternative dosing assessment in approximately 300 participants in the 6 year to < 12 year old age group to assess reactogenicity and immunogenicity of a lower dose regimen. No participants in Part 1 will participate in Part 2 or Part 3 of the study, and no participant in Part 2 will participate in Part 3 of the study.

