**Table 5: Pause Rule Criteria, Events, and Thresholds**

Pause Rule Criterion	Event	Participant Threshold for Triggering Study Pause
1	Any death due to SARS-CoV-2 infection	$\geq 1$
2	Any SAE or Grade 4 AE that cannot be reasonably attributed to a cause other than vaccination	$\geq 1$
3	ICU Admission due to COVID-19	$\geq 1$
4 	Individual Grade 3 or higher solicited local AR lasting $\geq 24$ hours and occurring within 7 days of injection (Days 1-7)	At least 2 participants and $\geq 5\%$ of the dosed participants in an age group
5 	Individual Grade 3 or higher solicited systemic AR lasting $\geq 24$ hours and occurring within 7 days of injection (Days 1-7)	At least 2 participants and $\geq 10\%$ of the enrolled participants in an age group
6 	Any $\geq$ Grade 3 or higher unsolicited AE that cannot be reasonably attributed to a cause other than vaccination	At least 2 participants and $\geq 5\%$ of the enrolled participants in an age group

Abbreviations: AE = adverse event; AR = adverse reaction; COVID-19 = coronavirus disease 2019; ICU = intensive care unit; SAE = serious adverse event; SARS-CoV-2 = severe acute respiratory syndrome coronavirus 2.

 “Individual AR” is defined as 1 AR type, eg, pain, erythema, or headache could each be an “individual AR.”

 Events in participants receiving booster doses will be considered separately from the events during the primary vaccination series.

If any of the thresholds for a study pause is met, the Sponsor will immediately suspend further enrollment and/or study dosing by notifying all investigators. Such a suspension will remain in force until the threshold events are reviewed by the DSMB and a recommendation to continue is provided to the Sponsor.

The investigator or designee is responsible for reporting to the Sponsor, via the electronic data capture (EDC) system, each event that potentially meets any pause rule criterion within 24 hours of observation. If an SAE assessed as related to IP by the investigator is reported at any point, the Sponsor’s medical monitor is responsible for a rapid assessment (with the Sponsor’s Medical and Safety team) of whether pause rule # 2 has been met; the Sponsor medical monitor may consult with the DSMB chair as an independent entity to make that determination, as described in the DSMB charter.

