**Table 8:      Solicited Adverse Reactions and Grades: Age 37 Months to < 12 years**

Reaction	Grade 0	Grade 1	Grade 2	Grade 3	Grade 4
Injection site pain	None	Does not interfere with activity	Interferes with activity	Prevents daily activity	Requires emergency room visit  or hospitalization
Injection site erythema (redness)	< 25 mm/ < 2.5 cm	25-50 mm/ 2.5-5 cm	51-100 mm/ 5.1-10 cm	> 100 mm/ > 10 cm	Necrosis or exfoliative dermatitis
Injection site swelling/induration (hardness)	< 25 mm/ < 2.5 cm	25-50 mm/ 2.5-5 cm	51-100 mm/ 5.1-10 cm	> 100 mm/ > 10 cm	Necrosis
Axillary (underarm) swelling or tenderness ipsilateral to the side of injection	None	No interference with activity	Some interference with activity	Prevents daily activity	Emergency room visit  or hospitalization
Headache	None	No interference with activity	Some interference with activity	Significant; Prevents daily activity	Requires emergency room visit  or hospitalization
Fatigue	None	No interference with activity	Some interference with activity	Significant; prevents daily activity	Requires emergency room visit  or hospitalization
Myalgia (muscle aches all over body)	None	No interference with activity	Some interference with activity	Significant; prevents daily activity	Requires emergency room visit  or hospitalization
Arthralgia (joint aches in several joints)	None	No interference with activity	Some interference with activity	Significant; prevents daily activity	Requires emergency room visit  or hospitalization
Nausea/vomiting	None	No interference	Some interference	Prevents daily activity,	Requires emergency room visit  or

Reaction	Grade 0	Grade 1	Grade 2	Grade 3	Grade 4 
		with activity or 1-2 episodes/ 24 hours	with activity or > 2 episodes/ 24 hours		hospitalization for hypotensive shock
Chills	None	No interference with activity	Some interference with activity not requiring medical intervention	Prevents daily activity and requires medical intervention	Requires emergency room visit  or hospitalization
Fever	< 38.0°C < 100.4° F	38.0-38.4°C 100.4-101.1°F	38.5-38.9°C 101.2-102.0°F	39.0-40.0°C 102.1-104.0°F	> 40.0°C > 104.0°F

 Age at time of enrollment determines the scale to be used.

 Grading for Grade 4 events per investigator assessment (with exception of fever).

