**Table 9: Solicited Adverse Reactions and Grades: Age 6 Months to ≤ 36 Months**

Reaction	Grade 0	Grade 1	Grade 2	Grade 3	Grade 4 
Local Reaction					
Injection site pain/tenderness	None	Mild discomfort to touch or some pain but no interference with normal daily activities	Cries when limb is moved/refuses to move limb or pain interferes with normal daily activities	Significant pain at rest or pain prevents normal daily activities	Requires emergency room visit  or hospitalization
Injection site erythema (redness)	< 5 mm/ < 0.5 cm	5-20 mm/ 0.5-2.0 cm	> 20-50 mm > 2.0-5.0 cm	> 50 mm/ > 5 cm	Necrosis or exfoliative dermatitis
Injection site swelling/induration (hardness)	< 5 mm/ < 0.5 cm	5-20 mm/ 0.5-2.0 cm	> 20-50 mm > 2.0-5.0 cm	> 50 mm/ > 5 cm	Necrosis

Reaction	Grade 0	Grade 1	Grade 2	Grade 3	Grade 4 
Groin or underarm swelling or tenderness ipsilateral to the side of injection	None	Some swelling or tenderness but no interference with normal daily activities	Swelling or tenderness that interferes with normal daily activities	Swelling or tenderness that prevents normal daily activities	Emergency room visit  or hospitalization
Systemic Reaction					
Fever	< 38.0°C	38.0-38.4°C 100.4-101.1°F	38.5-39.5°C 101.2-103.1°F	39.6-40.0°C 103.2-104.0°F	> 40.0°C > 104.0°F
Irritability/crying	None	Lasting < 1 hour or easily consolable	Lasting 1-3 hours or requiring increased attention	Lasting > 3 hours or inconsolable	Requires emergency room visit  or hospitalization
Sleepiness	None	Sleepier than usual or less interested in surroundings	Not interested in surroundings or sleeps through meals	Sleeps most of the time, hard to arouse	Inability to arouse
Loss of appetite	None	Eating less than normal for 1-2 feeds/meals	Missed 1-2 feeds/ meals completely	Missed > 2 feeds/meals completely or refuses most feeds/meals	Requires emergency room visit  or hospitalization

 Age at time of enrollment determines the scale to be used.

 Grading for Grade 4 events per investigator assessment (with exception of fever).

 Emergency room visit includes urgent care visit.

Source: Guidance for industry – Toxicity Grading Scale for Healthy Adult and Adolescent Volunteers Enrolled in Preventative Vaccine Clinical Trials ([DHHS 2007](#)).

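### The 2 to <6 years group is assessed on two different solicited-reaction scales but is tabulated, and counted in the pause rules, as one group

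*Protocol*

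**What the plan says.** - **Age groups (Protocol Section 3.1).** "The study population will be divided into 3 age groups": 6 to <12 years, 2 to <6 years, and 6 months to <2 years.
- **Scales (Section 7.4.3).** Table 8 is headed "Solicited Adverse Reactions and Grades: Age 37 Months to < 12 years" and Table 9 "Solicited Adverse Reactions and Grades: Age 6 Months to ≤ 36 Months". A footnote to both tables says: "Age at time of enrollment determines the scale to be used". The oldest group therefore lies wholly on Table 8 and the youngest wholly on Table 9. Only 2 to <6 years uses both.
- **Tabulation (Section 8.5.2).** "All safety analyses will be provided by vaccination group (dose levels of mRNA-1273 and placebo) and by age group". The rows are any local, any systemic and any solicited reaction, by toxicity grade, after each injection. Table 11 adds a 95% CI. The section also says that participants "in different age groups who receive the same mRNA-1273 dose level may be combined for safety analysis".
- **Analysis set (Table 10).** The Solicited Safety Set takes everyone in the Safety Set with any solicited data, whichever scale produced it.
- **Pause rules (Section 6.4, Table 5).** Rule 4 concerns a Grade 3 or higher solicited local reaction and needs at least 2 participants and at least 5% of those dosed in an age group. Rule 5 concerns a systemic one and needs at least 2 participants and at least 10% "of the enrolled participants in an age group". A footnote defines the unit as a single reaction type.

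The protocol nowhere separates the 2 to <6 years group by scale.

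**The concern.** A percentage by grade can be interpreted only if the grade means the same for every child in the denominator. In the 2 to <6 years group it does not, because the two scales ask about different symptoms and draw the grade lines in different places.

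Solicited reactions are a primary safety endpoint. In this age group they also inform the choice among Part 1 arms of about 75 children per dose, which are not randomised against each other. If the share of children under 37 months differs between two arms, their rates can differ with no difference in reactogenicity.

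The pause rules raise a separate difficulty. For a systemic reaction listed on only one table, the rule 5 denominator includes children who could not have that reaction recorded as a solicited item.

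**Working it through.** **1. The two scales side by side**

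| Item | Table 8 (from 37 months) | Table 9 (up to 36 months) |
|---|---|---|
| Systemic items | headache, fatigue, myalgia, arthralgia, nausea/vomiting, chills, fever | fever, irritability/crying, sleepiness, loss of appetite |
| Erythema or swelling, Grade 1 starts at | 25 mm | 5 mm |
| Erythema or swelling, Grade 3 | >100 mm | >50 mm |
| Fever, Grade 3 | "39.0-40.0°C 102.1-104.0°F" | 39.6-40.0°C |

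The same finding can therefore receive different grades:
- Redness of 15 mm is Grade 0 on Table 8 and Grade 1 on Table 9.
- Redness of 60 mm is Grade 2 on Table 8 and Grade 3 on Table 9.
- A temperature of 39.3°C is Grade 3 on Table 8 and Grade 2 on Table 9.

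Table 9 is stricter for erythema and swelling and more lenient for Grade 3 fever, so the net error has no fixed sign. Fever agrees at its lowest cut (38.0°C) and at Grade 4 (>40.0°C). Only the boundary between Grades 2 and 3 differs.

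**2. Effect on a tabulated rate**

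Let f be the share of the group on Table 9, and R9 and R8 the rates on each scale. The reported rate is f × R9 + (1 − f) × R8. Two arms with identical reactogenicity but shares f1 and f2 differ by (f1 − f2) × (R9 − R8). With f1 = 0.40 and f2 = 0.15, that is 2.5 percentage points for every 10 points by which the scales differ.

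**3. Share on Table 9**

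The protocol gives no age mix, so f is an assumption. Uniform ages over 48 months give 12/48 = 25% to 13/48 = 27%, depending on how the month of age 36 is counted. The range taken is 15 to 40%.

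**4. What rule 5's 10% means for single-scale systemic items**

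The rate needed among the children asked is 0.10/f for a Table 9-only item and 0.10/(1 − f) for a Table 8-only item.

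| f | Table 9-only item | Table 8-only item |
|---|---|---|
| 15% | 66.7% | 11.8% |
| 25% | 40.0% | 13.3% |
| 27% (13/48) | 36.9% | 13.7% |
| 40% | 25.0% | 16.7% |

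A larger group does not remove this. With f = 25% and 4,000 children, the trigger is 400 events, and 400 of 1,000 on Table 9 is still 40%.

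**5. Illustration with 75 children**

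The trigger is max(2, ⌈0.10 × 75⌉ = 8) participants. Take a true Grade 3 or higher rate of 20% among those asked. The entries are exact binomial probabilities of meeting the count. The second figure applies the same 10% (and at least 2) to the children asked only.

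| f (children on Table 9 / Table 8) | Table 9-only: whole group vs children asked | Table 8-only: whole group vs children asked |
|---|---|---|
| 15% (11 / 64) | 0.02% vs 67.8% | 95.8% vs 98.2% |
| 25% (19 / 56) | 2.3% vs 91.7% | 89.6% vs 97.9% |
| 40% (30 / 45) | 23.9% vs 95.6% | 70.3% vs 96.2% |

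This shows how much the denominator matters. It does not propose a rule: with 19 children asked, 10% amounts to 2 children, and a true rate of 10% would already meet that count with probability 58.0%.

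**The case against.** **The SAP may split the tables.** Section 8.5.2 defers detail to the SAP, which is not at hand, and the protocol fixes no denominator for individual reactions. This stands for item-level tables, and nobody should infer that such rows will certainly be diluted. It does not remove the stated method, which reports composite rates by grade for the age group from one analysis set. Nor would a SAP change Table 5, which sits in the protocol.

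**The Part 2 comparison is safe.** A reader might infer that the vaccine-placebo contrast is biased. The documents do not support that. Randomisation is 3:1 within age group (Section 5.2), so the mix of scales is balanced in expectation. The exposure is in absolute rates and Part 1 comparisons.

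**No dose is chosen from one percentage.** Part 1 is for estimation, and the internal safety team and the DSMB review all the available safety data. This limits the consequence but does not make the percentages comparable.

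**Dilution is not general.** The four local reactions and fever are on both scales. Their fault is mixed cut-offs, and every child contributes to the composites. Dilution reaches only single-scale systemic items under rule 5.

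**Combining age groups is only permitted.** That is so, but Table 3 has 50 µg in all three age groups (Arms 1, 3 and 6), so the permission could mix scales outright. It extends only to the same dose level; the plan does not pool across dose levels.

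**Boosters.** A reader might suppose that many children are later graded on a scale they have outgrown. Keeping the enrollment-age scale is an explicit choice, and it affects only Part 1 children boosted with mRNA-1273 under Amendment 7. Part 2 children under 6 years were not offered that booster, and no eDiary follows mRNA-1273.214 (Section 7.4.3).

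**Rules 4 and 5 have little remaining reach.** Amendment 9 records all age groups as unblinded, and the cross-over schedule (Table 13) has no solicited-reaction diary. Rule 2 also acts on a single SAE or Grade 4 event that cannot reasonably be attributed to another cause. This stands and makes the pause-rule part the less pressing one.

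**Conclusion.** The point holds in limited form. In the 2 to <6 years group, the planned any-reaction and by-grade percentages combine two scales with different systemic items and different cut-offs. This affects absolute rates, comparisons between the Part 1 dose arms, and any combination of age groups that crosses the scales. The direction varies by reaction, so the rates cannot be called simply too low or too high.

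For rule 5, the size depends wholly on the assumed age mix. Over a 15 to 40% share on Table 9, the nominal 10% becomes about 25 to 67% of the children asked for irritability, sleepiness or loss of appetite. For items found only on Table 8 it becomes about 12 to 17%. No single value in those ranges is established by the protocol. Higher figures follow only if placebo recipients are also assumed never to have a Grade 3 reaction, which the documents do not say.

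**What to change.** In Section 8.5.2 and Table 11:

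- Present solicited reactions for 2 to <6 years by grading scale, as 24 to 36 months and 37 months to <6 years.
- Use as the denominator for each reaction only the children solicited for it.
- Do not combine age groups across scales for solicited reactions.

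The cost is analysis wording and one further table split, since age at enrollment is already recorded. The price is smaller denominators per row, and so wider intervals.

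Separately, the rule 4 and 5 denominators in Table 5 must be reconciled with the two scales by the sponsor and the DSMB. No threshold is proposed here.
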